where $\hat{\beta}_{1i}$ is the estimated slope prior to the estimated inflection point $\hat{\kappa}_i$, and $\hat{\beta}_{2i}$ is the estimated slope after the estimated inflection point $\hat{\kappa}_i$. The parameters of main interest include the slopes $\hat{\beta}_{1i}$ and $\hat{\beta}_{2i}$, and the inflection points, $\hat{\kappa}_i$, and can be readily estimated using least squares. If the linear regression model is selected, the average change in log CFU count per day over 14 days will be estimated by the constant linear regression slope over time, $\hat{\beta}_i$. $BA_{CFU}(0-14)$ will be calculated for each patient within a treatment group individually, and then used as the response variable in an ANCOVA model, with a fixed effect for treatment group and screening log CFU count as a covariate. Treatment group means from the ANCOVA model will be used to quantify the evidence that each of the treatment group mean $BA_{CFU}(0-14)$ is less than 0 (i.e., that the treatment group mean has a negative slope on average).

Multiplicity will be handled by means of a step-down sequential approach. The five TBA-7371 treatment regimens will be divided into 3 testing groups: Group 1 = Cohort V (400 mg QD) and Cohort IV (100 TID); Group 2 = Cohort III (200 mg QD) and Cohort II (100 BID); and Group 3 = Cohort 1 (100 QD). Group 1, or the group with the highest dose cohort allowed by the IDMC will be tested first using a Hochberg multiplicity adjustment: if the maximum and minimum one-sided p-values are ≥ 0.05 and ≥ 0.025 , respectively, formal testing will be stopped and all cohorts below will be declared a failure; if the maximum and minimum one-sided p-values are ≥ 0.05 and < 0.025 , formal testing will be stopped but the regimen with p-value < 0.025 will be declared a success; if the maximum and minimum one-sided p-values are < 0.05 and < 0.025 , both cohorts will be declared a success and testing will proceed to Group 2 regimens with the same step-down approach to continue until a failed cohort is observed.

Primary efficacy analyses will be performed in the modified Intention-to-Treat (mITT) population.

The study will be declared a success if at least one of the TBA-7371 treatment groups achieves a statistically significant 1-sided p-value and demonstrates an acceptable safety profile.

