9.2. Sample Size Determination

Approximately 90 participants will be randomized 5:1 to either intervention arm, totaling $N = 15$ for each TBA-7371 treatment and control groups.

Bactericidal effect

Based on Diacon et al. (2013)³, standard deviations associated with $BA_{CFU}(0-14)$ were relatively consistent across 5 treatment groups, ranging from 0.05 to 0.08. If we assume conservatively that the true SD of the $BA_{CFU}(0-14)$ measures for the TBA-7371 treatment groups is equal to 0.1, then with $N=15$ per group we have 80% (90%) power to detect a true group mean $BA_{CFU}(0-14)$ reduction of 0.067 (0.079), using a 1-sided alpha = 5%. For reference, the observed $BA_{CFU}(0-14)$ reduction in Diacon et al, 2013³ were 0.040, 0.056, 0.077, 0.104, and 0.112 for Bedaquiline 100 mg, 200 mg, 300 mg, 400 mg and standard HRZE, respectively.

Safety

With $N=15$ per group, we have approximately 80% (90%) probability to observe at least one AE if the true AE rate is 10% (15%). We have only 54% probability to observe at least one AE if the true AE rate is 5%. Across the five TBA-7371 treatment groups ($N=75$), we have 90% probability to observe at least one AE if the true AE rate is 3.0%.

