where $\hat{\beta}_{1i}$ is the estimated slope prior to the estimated inflection point $\hat{\kappa}_i$, and $\hat{\beta}_{2i}$ is the estimated slope after the estimated inflection point $\hat{\kappa}_i$. The parameters of main interest include the slopes $\hat{\beta}_{1i}$ and $\hat{\beta}_{2i}$, and the inflection points, $\hat{\kappa}_i$, and can be readily estimated using least squares. If the linear regression model is selected, the average change in \log_{10} CFU count per day over 14 days will be estimated by the constant linear regression slope estimate, $\hat{\beta}_i$. $BA_{CFU}(0-14)$ will be calculated for each patient within a treatment group individually, and then used as the response variable in an ANCOVA model, with a fixed effect for treatment group and screening \log_{10} CFU count as a covariate. Treatment group means from the ANCOVA model will be used to quantify

the evidence that each of the treatment group mean BA_{CFU}(0-14) is less than 0 (i.e., that the treatment group mean has a negative slope on average). The mITT population will be used for the primary efficacy analysis.

Multiplicity will be handled by means of a step-down sequential approach. The five TBA-7371 treatment regimens will be divided into 3 testing groups: Group 1 = Cohort V (400 mg QD) and Cohort IV (100 TID); Group 2 = Cohort III (200 mg QD) and Cohort II (100 BID); and Group 3 = Cohort 1 (100 QD). Group 1, or the group with the highest cohort allowed by the IDMC will be tested first using a Hochberg multiplicity adjustment: if the maximum and minimum one-sided p-values are ≥ 0.05 and ≥ 0.025 , respectively, formal testing will be stopped and all cohorts below will be declared a failure; if the maximum and minimum one-sided p-values are ≥ 0.05 and <0.025 , formal testing will be stopped but the regimen with p-value < 0.025 will be declared a success; if the maximum and minimum one-sided p-values are < 0.05 and <0.025 , both cohorts will be declared a success and testing will proceed to Group 2 regimens with the same step-down approach to continue until a failed cohort is observed.

The study will be declared a success if at least one of the TBA-7371 treatment groups achieves a statistically significant 1-sided p-value and demonstrates an acceptable safety profile.

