6.2 Sample Size Determination

Anticipating all cohorts are to be assessed in the study, approximately 90 participants will be randomized in a 5:1 ratio to either TBA-7371 or control group, totaling N = 15 participants for each TBA-7371 treatment and control groups (receiving treatment with HRZE).

Bactericidal effect

Based on Diacon et al. (Diacon, 2013) standard deviations associated with BAcfu(0-14) were relatively consistent across 5 treatment groups, ranging from 0.05 to 0.08. If we assume conservatively that the true standard deviation of the BAcfu(0-14) measures for the TBA-7371 treatment groups is equal to 0.1, then with N = 15 per group we have 80% (90%) power to detect a true group mean BAcfu(0-14) reduction of 0.067 (0.079), using a 1-sided alpha = 5%. For reference, the observed BAcfu(0-14) reduction in Diacon et al, 2013 were 0.040, 0.056, 0.077, 0.104, and 0.122 for Bedaquiline 100 mg, 200 mg, 300 mg, 400 mg and standard HRZE, respectively.

Safety

With N = 15 per group, we have approximately 80% (90%) probability to observe at least one AE if the true AE rate is 10% (15%). We have only 54% probability to observe at least one AE if the true AE rate is 5%. Across the five TBA-7371 treatment groups (N=75), we have 90% probability to observe at least one AE if the true AE rate is 3.0%.

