6. HRZE QD

The nomenclatures of study interventions will be used to display in tables, figures, and listings.

All measured variables and derived parameters will be listed individually and, if appropriate, tabulated using descriptive statistics. For categorical variables, summary tables will be provided giving sample size, absolute and relative frequency. For continuous variables, summary tables will be provided giving sample size, arithmetic mean, geometric mean (if appropriate), standard deviation, coefficient of variation (if appropriate), median, minimum and maximum. For variables with non-normal distribution, medians and interquartile range will be calculated, and the appropriate non-parametric tests will be applied. Unless specified otherwise, all confidence intervals will be two-sided 95% confidence intervals. Given the primary endpoint is tested using a one-sided test at 0.05, the corresponding 90% confidence interval will be provided. One-sided p-value will be displayed with 4 decimal places; if the p-value is less than 0.0001, display as “<0.0001”.

Change from baseline or screening for a measured variable at a particular post-baseline time point will be computed as the value at the post-baseline time point minus the baseline or screening value, as appropriate.

Percentages will be displayed with one decimal place and percentages for zero counts will be omitted from the presented results. If the percentage is greater than 0 but rounds to 0.0% (e.g. 0.04%), display as “(<0.1)”.

SAS code of SAS procedures that will be used to perform efficacy and safety analyses is provided in [Appendix 4](#).

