Multiplicity will be handled by means of a step-down sequential approach. The five TBA-7371 treatment regimens will be divided into 3 testing groups: Group 1 = Cohort V (400 mg QD) and Cohort IV (100 TID); Group 2 = Cohort III (200 mg QD) and Cohort II (100 BID); and Group 3 = Cohort 1 (100 QD). Group 1, or the group with the highest cohort allowed by the IDMC will be tested first using a Holmberg multiplicity adjustment: if the maximum and minimum one-sided p-values are ≥ 0.05 and ≥ 0.025 , respectively, formal testing will be stopped and all cohorts below will be declared a failure; if the maximum and minimum one-sided p-values are ≥ 0.05 and < 0.025 , formal testing will be stopped but the regimen with p-value < 0.025 will be declared a success; if the maximum and minimum one-sided p-values are < 0.05 and < 0.025 , both cohorts will be declared a success and testing will proceed to Group 2 regimens with the same step-down approach to continue until a failed cohort is observed.

The study will be declared a success if at least one of the TBA-7371 treatment groups achieves a statistically significant 1-sided p-value and demonstrates an acceptable safety profile.

Geometric mean and geometric mean ratio of post-baseline to baseline of CFU/mL counts with 95% confidence interval (CI) at each time point will be presented in line plots by treatment group. In addition, observed and fitted lines of bilinear and linear regression models of $\log_{10}\text{CFU}/\text{mL}$ counts over time will be presented for each participant.

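### The primary step-down rule gives no outcome when both p-values, or a lone cohort's p-value, fall in [0.025, 0.05), where Hochberg would declare success

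*SAP*

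**What the plan says.** The five regimens are tested in order: Group 1 (Cohorts V and IV), Group 2 (Cohorts III and II), Group 3 (Cohort I alone). Protocol 1.1.9.1 says that "the group with the highest dose cohort allowed by the IDMC will be tested first using a Hochberg multiplicity adjustment", and Protocol 9.4.1.1 names the same method. The SAP copy of the rule (11.1.1) reads "will be tested first using a Holmberg multiplicity adjustment"; that may be a text-reading error, and SAP section 8 declares no change from the protocol's analyses.

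All three places then spell out the same branches:

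- larger p at least 0.05 and smaller p at least 0.025: stop, failure;
- larger p at least 0.05 and smaller p below 0.025: stop, the regimen with the smaller p succeeds;
- larger p below 0.05 and smaller p below 0.025: "both cohorts will be declared a success and testing will proceed to Group 2 regimens with the same step-down approach".

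No separate rule is given for a group with one cohort. SAP 9.1 states the overall level: "Given the primary endpoint is tested using a one-sided test at 0.05, the corresponding 90% confidence interval will be provided". The ANCOVA code in SAP Appendix 4 uses alpha = 0.05 for every regimen.

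**The concern.** Two thresholds on two p-values make four combinations, and only three are written. The missing one is larger p below 0.05 with smaller p at least 0.025. It is also the only region where Hochberg and Holm disagree for two tests: Hochberg rejects both hypotheses, Holm neither. The success branch as written, with its extra condition on the smaller p, is Holm's condition for rejecting both. The procedure's name therefore points one way and the written condition the other.

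For a lone cohort the larger and smaller p-values coincide. A value such as 0.03 then fits no branch, and a literal reading of the success branch would require p below 0.025.

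These branches decide which regimens are a primary success and whether the next group is tested. In the first group tested they also decide whether the efficacy half of the study-success criterion is met. Sponsor and CRO staff are unmasked, so a reading chosen once the p-values are known would be open to challenge.

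**Working it through.** **Coverage of the rule for two cohorts**

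| Larger p | Smaller p | Written outcome | Hochberg | Holm |
|---|---|---|---|---|
| ≥ 0.05 | ≥ 0.025 | stop, failure | neither | neither |
| ≥ 0.05 | < 0.025 | stop, one success | one | one |
| < 0.05 | < 0.025 | both, continue | both | both |
| < 0.05 | ≥ 0.025 | **none** | **both** | **neither** |

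For a single p-value, 0.02 matches the third row, 0.06 matches the first and 0.04 matches none. Hochberg and Holm with one test both reject at 0.05.

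**Inputs** (Protocol 9.2, SAP 6.2): SD 0.1, n = 15 per regimen, one-sided 0.05, reductions of 0.067 and 0.079.

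**Reproducing the stated power.** One-sample t-test, noncentral t with 14 df and noncentrality δ√15/0.1:

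| δ | P(p < 0.05) | P(p < 0.025) | Band = difference | Band² (pair) |
|---|---|---|---|---|
| 0.067 | 0.7943 | 0.6752 | 0.1192 | 0.0142 |
| 0.079 | 0.8965 | 0.8118 | 0.0847 | 0.0072 |

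The second column agrees with the stated 80% and 90%. A lone cohort that is tested therefore lands in the unwritten band 11.9% or 8.5% of the time. A pair does so 1.4% or 0.7% of the time, taking the two p-values as independent.

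**Through the sequence, all cohorts opened, 0.067 in each.** The written both-succeed branch has probability 0.7943² − 0.0142 = 0.6168. The chance of reaching an unwritten result is:

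- Group 1: 0.0142
- Group 2: 0.6168 × 0.0142 = 0.0088
- Group 3: 0.6168² × 0.1192 = 0.0453
- Total: 0.068

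With 0.079 in each: 0.0072 + 0.7966 × 0.0072 + 0.7966² × 0.0847 = 0.067.

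As an assumed dose trend, the bedaquiline reference values in Protocol 9.2 can be assigned as 0.104, 0.077, 0.056, 0.056 and 0.040 to Cohorts V, IV, III, II and I. This gives 6.6%.

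**Cohort V not opened.** Group 1 is Cohort IV alone: 0.1192 + 0.6752 × 0.0142 + 0.6752 × 0.6168 × 0.1192 = 0.178. The other two scenarios give 14.5% and 14.9%.

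**Pooled ANCOVA error** (90 − 6 groups − 1 covariate = 83 df): 5.8% at 0.067 and 5.0% at 0.079.

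**SD at the ends of the cited 0.05–0.08 range** (14 df, all cohorts opened): equal 0.067 gives 6.0% at SD 0.08 and 0.2% at SD 0.05; the assumed trend gives 10.3% and 8.1%.

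**Power for at least one regimen, Hochberg against reading the gap as no success:**

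- 0.067: 1 − (1 − 0.6752)² + 0.0142 = 90.9%, against 89.5%
- 0.079: 97.2%, against 96.5%

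**Type I error.** Under the global null with independent p-values, the chance of any false success is 1 − 0.975² + 0.025² = 5.00% under Hochberg and 1 − 0.975² = 4.94% if the gap is read as no success.

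**The case against.** The strongest reply is that the plan already names a complete method. Hochberg is fully defined for two tests and for one, SAP section 8 declares no departure from the protocol, and SAP 9.1 sets the one-sided level at 0.05. On that view the extra condition on the smaller p-value is a slip in transcription. The rule speaks of a maximum, a minimum and two cohorts, so it was never meant for a lone p-value. Hochberg is indeed the probable intent. But the written branch contradicts it, and a literal application withholds a success that Hochberg grants. For Group 3 the text carries forward the same approach without saying how it applies to one p-value.

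The second reply concerns size, and most of it stands. Of the 6.8%, 4.5 points come from Group 3, which is reached only after earlier regimens have succeeded, so study-level efficacy is already secured. The gap for pairs accounts for 2.3 points. With all cohorts opened, the study criterion is exposed in only 1.4% of trials at 0.067, 0.7% at 0.079 and 0.2% under the assumed trend. If Cohort V is not opened, though, the first test is a lone cohort and the exposure at 0.067 is 11.9%. The estimates also move considerably with the SD.

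The printed name in the SAP may be a reading artefact, and the point does not depend on it.

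**Conclusion.** The concern holds. The primary decision rule omits one of four possible outcomes for a pair, sets no threshold for a single-cohort group, and words its success branch as Holm's condition although the protocol names Hochberg.

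At the design SD of 0.1, about 5% to 7% of trials with all cohorts opened would reach an unwritten result, and about 15% to 18% if Cohort V is not opened (14 df). These figures assume independent p-values for the 14 df formulae and either equal effects or the stated trend. Simulation with shared ANCOVA error gave the same 5.8% and 5.0% at 83 df. The consequence is a lost or disputed regimen-level success, and occasionally a disputed study-level one. It is not a false-positive problem, and the stated 80% and 90% power figures are correct as per-regimen power at one-sided 0.05. The change should be made, but the validity of the design does not hang on it.

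**What to change.** In SAP 11.1.1, replace the third branch with: *if the larger one-sided p-value is below 0.05, both cohorts are declared a success and testing proceeds to the next group.* Add: *a group with one cohort is tested at one-sided 0.05, and testing proceeds only if that cohort succeeds.* Name the method as Hochberg, correcting the SAP's printed name if the source file has it.

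A SAP clarification is enough, because the protocol already names the method; its two copies of the rule can be aligned at the next amendment. The wording should be fixed before the primary p-values are produced.

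The cost is two sentences, with no added participants or analyses. Family-wise error stays at 5%: a later group is tested only when every regimen in the earlier group has been rejected, so a false success there requires that any true null in the earlier group was already rejected.

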11.1.2 Secondary Analysis

EBA measures $BA_{CFU}(0-2)$ and $BA_{CFU}(2-14)$ will be calculated from the bilinear regression model and assessed similarly as described for $BA_{CFU}(0-14)$ in [Section 11.1.1](#). There will be no adjustment for multiple comparisons and no formal success criteria for all secondary EBA measurements.

In order to estimate $BA_{CFU}(0-2)$ and $BA_{CFU}(2-14)$, the parameter κ is fixed at 2 so that the bilinear model used becomes

$$\log_{10} CFU/mL = \alpha - \beta_{1i} \cdot t + \varepsilon; \quad t \leq 2;$$

$$\log_{10} CFU/mL = \alpha + (\beta_{2i} - \beta_{1i}) \cdot 2 - \beta_{2i} \cdot t + \varepsilon; \quad t > 2$$

and therefore we have for participant i that

$$BA_{CFU}(0-2)_i = \hat{\beta}_{1i}$$

and

$$BA_{CFU}(2-14)_i = \hat{\beta}_{2i}.$$

11.1.3 Sensitivity Analysis

Two approaches will be conducted as sensitivity analysis of CFU efficacy analysis.

11.1.3.1 ANCOVA model using average change from baseline

Given that treatment ends on Day 14, $BA_{CFU}(0-14)$ of $\log_{10}CFU/mL$ counts over 14 days of treatment will be estimated by calculating an average of the change from baseline to day 14 in log of CFU as follows:

$$BA_{CFU}(0-14)_i = \frac{\log_{10}(CFU/mL)_{14} - \log_{10}(CFU/mL)_{base}}{14}.$$

An ANCOVA model will be fitted as done in [Section 11.1.1](#). If the CFU is missing at Day 14, then the latest time point with a measurement with the corresponding denominator will be used, e.g. if the latest day with a CFU measurement is Day 10, then the divisor in the formula above will be 10.

11.1.3.2 Random intercepts and slopes model across all data points

A mixed model with random intercepts and slopes will be fitted in order to estimate the average change from baseline to Day 14. It will use all log CFU data points for all participants and time points. The model is given by

$$\log_{10} CFU/mL = \alpha + u_i + (\beta_1 + b_i)t + \beta_{2j}X_{1j} + \beta_{3j}X_{1j}t + \beta_4X_{2i} + \varepsilon_{ij}$$

where $t = 0, 1, \dots, 14$, X_{1j} is the dummy indicator for treatments $j = 1, \dots, 5$ with HRZE as the reference group, X_{2i} the covariate for baseline $\log_{10}\text{CFU/mL}$, u_i the random intercepts with distribution $u_i \sim N(0, \sigma_u^2)$, b_i the random slopes with distribution $b_i \sim N(0, \sigma_b^2)$ and $\varepsilon_{ij} \sim N(0, \sigma^2)$. An unstructured covariance structure will be used for the variance-covariances of the random effects. It may be simplified to variance components (option “vc”) if the former doesn’t yield convergence or there is no gain in model fit as decided through the AIC. The fixed effects of the model are given by day t , treatment group X_j , baseline $\log_{10}\text{CFU/mL}$ and the interaction between time and treatment group.

The average slope over time for each treatment group will be estimated and reported with 90% confidence intervals using the time and interaction effects, i.e.

$$(\hat{\beta}_1 + \hat{\beta}_{3j}).$$

11.2 Secondary Efficacy Endpoints

11.2.1 Time to Sputum Culture Positivity

When time to sputum culture positivity for a participant is not concluded by Day 42 (i.e., > 42 days), the value will be defined to be 43 days. For each participant, linear and bilinear regression models will be fit, and the better fit model based on lower AIC similarly as described for BACFU(0-14) in [Section 11.1.1](#) will be used to estimate BATTP(0-14), BATTP(0-2) and BATTP(2-14) of TTP from Screening to Day 14, Screening to Day 2 and Day 2 to Day 14, respectively. BATTP(0-14), BATTP(0-2) and BATTP(2-14) will be analyzed using an ANCOVA model, with a fixed effect for treatment group and baseline TTP as a covariate. An ANCOVA model will be used to quantify the evidence that each of the treatment group mean BATTP(0-14), BATTP(0-2) and BATTP(2-14) is less than 0.

Mean and mean change from baseline of TTP with 95% CI at each time point will be presented in line plots by treatment group. In addition, observed and fitted lines of bilinear and linear regression models of TTP over time will be presented for each participant.

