Slope i.e. average change per day from screening (“0”) to Day 2 [$BA_{CFU}(0-2)$] and from Day 2 to Day 14 [$BA_{CFU}(2-14)$] of the log CFU counts.	For each patient, linear and bilinear regression models will be fit, and the better fit model based on lower AIC will be used to estimate $BA_{CFU}(0-2)$ and $BA_{CFU}(2-14)$ of log CFU counts from screening to Day 2 and Day 2 to Day 14, respectively. An ANCOVA model will be used to quantify the evidence that the each of the treatment group means $BA_{CFU}(0-2)$ and $BA_{CFU}(2-14)$ is less than 0.
Slope of the time to sputum culture positivity (TTP) in the MGIT system from screening to Day 14 [$BA_{TTP}(0-14)$], from screening to Day 2 [$BA_{TTP}(0-2)$], and from Day 2 to Day 14 [$BA_{TTP}(2-14)$].	For each patient, linear and bilinear regression models will be fit, and the better fit model based on lower AIC will be used to estimate $BA_{TTP}(0-14)$, $BA_{TTP}(0-2)$ and $BA_{TTP}(2-14)$ of TTP from screening to Day 14, screening to Day 2 and Day 2 to Day 14, respectively. An ANCOVA model will be used to quantify the evidence that the each of the treatment group means $BA_{TTP}(0-14)$, $BA_{TTP}(0-2)$ and $BA_{TTP}(2-14)$ is less than 0.

Endpoint	Statistical Analysis
Slope of the log concentration of sputum LAM from screening to Day 14 [$BA_{LAM}(0-14)$], from screening to Day 2 [$BA_{LAM}(0-2)$], and from Day 2 to Day 14 [$BA_{LAM}(2-14)$].	For each patient, linear and bilinear regression models will be fit, and the better fit model based on lower AIC will be used to estimate $BA_{LAM}(0-14)$, $BA_{LAM}(0-2)$ and $BA_{LAM}(2-14)$ of log concentration of sputum LAM from screening to Day 14, screening to Day 2 and Day 2 to Day 14, respectively. An ANCOVA model will be used to quantify the evidence that the each of the treatment group means $BA_{LAM}(0-14)$, $BA_{LAM}(0-2)$ and $BA_{LAM}(2-14)$ is less than 0.
Secondary Safety	
Frequency of participants with adverse events (AEs) and frequency of AEs: overall, by seriousness, severity, body system, preferred term and relatedness to study drug.	The frequency of participants with and frequency of AEs will be summarized by treatment group. The incidence of AEs by seriousness, severity, body system, preferred term and relatedness to study drug will be summarized by treatment group.

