regression model for individual participants in each treatment group in order to ensure the Akaike information criteria (AIC) values for the linear and bilinear models are based on the same form of the likelihood function. Suggested starting values for the parameters are $(\alpha, \beta_1) = (6, 0)$ however a grid search approach can be followed to obtain sensible starting values.

If the linear regression model is selected, the average change in $\log_{10}\text{CFU}/\text{mL}$ count per day over 14 days will be estimated by the constant linear regression slope estimate, $\hat{\beta}_{1i}$, i.e.

$$BA_{CFU}(0 - 14)_i = \hat{\beta}_{1i}.$$

Therefore, for each participant, slopes will be estimated using both bilinear and simple linear regression models, and the better fit model based on lower AIC will be selected for that participant and used to estimate $BA_{CFU}(0-14)$. The $\log_{10}\text{CFU}/\text{mL}$ screening measurement used in the model will be the average of the two individual screening measurements. $BA_{CFU}(0-14)$ will be calculated for each participant within a treatment group individually, and then used as the response variable in an ANCOVA model, with a fixed effect for treatment group and screening $\log_{10}\text{CFU}/\text{mL}$ count as a covariate. Treatment group means from the ANCOVA model will be used to quantify the evidence that each of the treatment group mean $BA_{CFU}(0-14)$ is less than 0 (i.e., that the treatment group mean has a negative slope on average). The mITT population will be used for the primary efficacy analysis with analyses using the per-protocol population performed to assess the robustness of results. The SAS PROC MIXED procedure will be used to fit an ANCOVA model.

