11.2.2 Sputum Lipoarabinomannan

When a value of concentration of sputum LAM is < lower limit of quantification (LLOQ), the value will be defined to be half of LLOQ. For each participant, linear and bilinear regression models will be fit, and the better fit model based on lower AIC similarly as described for BACFU(0-14) in [Section 11.1.1](#) will be used to estimate BALAM(0-14), BALAM(0-2) and BALAM(2-14) of log concentration of sputum LAM from Screening to Day 14, Screening to Day 2 and Day 2 to Day 14, respectively. BALAM(0-14), BALAM(0-2) and BALAM(2-14) will be analyzed using an ANCOVA model, with a fixed effect for treatment group and baseline log value of concentration of sputum LAM as a covariate. An ANCOVA model will be used to quantify the evidence that each of treatment group mean BALAM(0-14), BALAM(0-2) and BALAM(2-14) is less than 0.

Geometric mean and geometric mean ratio of post-baseline to baseline of concentration of sputum LAM with 95% CI at each time point will be presented in line plots by treatment group. In addition, observed and fitted lines of bilinear and linear regression models of log concentration of sputum LAM over time will be presented for each participant.

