Appendix 4 SAS Code

SAS code for computing 95% confidence interval for single proportion based on the mid-P method:

```
proc freq data=<dataset> order=freq;
  tables category / binomial (CL=MIDP) alpha=0.05;
  weight Count;
run;
```

SAS code for response-exposure E_{max} model:

```
ods output fitstatistics=<Data with aic>;
ods output parameterestimates=<Data with slope estimates>;
proc nlmixed data=<dataset>;
  by <treatment group>;
  parms Emax=<numeric>
    EC50=<numeric>
    s2=<numeric>;
  mu=(Emax*Cmax) / (EC50+Cmax);
  model <Avg. Slope(0-14)> ~ normal(mu,s2);
run;
```

SAS code for bilinear regression model with κ as one of the parameters:

```
ods output fitstatistics=<Data with aic>;
ods output parameterestimates=<Data with slope estimates>;
ods output additionalestimates=<Data with BA(0-14) estimate>;
run;
proc nlmixed data=<dataset>;
  by <subject ID>;
  parms alpha=4 to 8 by 0.5    betal=-0.3 to 0.3 by 0.05
beta2=-0.3 to 0.3 by 0.05    kappa=2 to 10 by 1    s2=0.05 to 0.3
by 0.05 / best=1;
  bounds alpha >0,    1 < kappa < 14,    s2>0; * Add constraints to
parameters to improve convergence;
  if day <= kappa then mu = alpha + betal*day;
  else if day > kappa then mu = alpha + betal*kappa +
beta2*(day-kappa);
  model logCFU ~ normal(mu,s2);
  estimate 'BACfu(0-14)' (kappa*betal + (t_last-
kappa)*beta2)/t_last; *Estimate BA(0-14);
run;
```

SAS code for bilinear regression model with kappa fixed at 2:

```
ods output fitstatistics=<Data with aic>;
ods output parameterestimates=<Data with slope estimates>;
proc nlmixed data=<dataset>;
  by <subject ID>;
  parms alpha=4 to 8 by 0.5    beta1=-0.3 to 0.3 by 0.05
beta2=-0.3 to 0.3 by 0.05 s2=0.05 to 0.3 by 0.05 / best=1;
  bounds alpha >0,    s2>0; * Add constraints to parameters to
improve convergence;
  if day <= 2 then mu = alpha + beta1*day;
  else if day > 2 then mu = alpha + beta1*2 + beta2*(day-2);
  model logCFU ~ normal(mu,s2);
run;
```

SAS code for simple regression model:

```
ods output fitstatistics=<Data with aic>;
ods output parameterestimates=<Data with slope estimates>;
proc nlmixed data=<dataset>;
  by <subject ID>;
  parms alpha=4 to 8 by 0.5    beta1=-0.3 to 0.3 by 0.05    s2=0.05
to 0.3 by 0.05 / best=1;
  mu = alpha + beta1*day;
  model logCFU ~ normal(mu,s2);
run;
```

SAS code for ANCOVA (lsmeans statement used to estimate 90% CIs, lsmestimate statements used for one-sided 5% p-values, trt = treatment group with HRZE as reference):

```
proc mixed data=<dataset>;

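### The Day 0-2 and Day 2-14 slopes are estimated one way for CFU (node fixed at Day 2) and another way for TTP and LAM (AIC-chosen model, free node), so same-named secondary endpoints are not comparable

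*SAP*

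**What the plan says.** **CFU.** SAP 11.1.2 states that "the parameter κ is fixed at 2 so that the bilinear model used becomes" a curve with one slope up to Day 2 and another after it. BA_CFU(0-2) is the first slope and BA_CFU(2-14) the second. No AIC choice enters. Appendix 4 has code for this model, with log CFU as the response.

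**TTP and LAM.** SAP 11.2.1 (TTP) and 11.2.2 (LAM) refer to 11.1.1, not 11.1.2. For TTP, the slopes come from "the better fit model based on lower AIC similarly as described for" the CFU (0-14) slope, and that one choice feeds the (0-14), (0-2) and (2-14) slopes. LAM has the same rule: "linear and bilinear regression models will be fit, and the better fit model based on lower AIC similarly as described for" that CFU slope.

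**What 11.1.1 does.** The choice is made person by person: "the better fit model based on lower AIC will be selected for that participant". If the line wins, the average daily change "will be estimated by the constant linear regression slope estimate". If the bilinear model wins, its node is estimated between Days 1 and 14 (Appendix 4: "SAS code for bilinear regression model with κ as one of the parameters"). The only averaging formula in 11.1.1 covers Day 0 to Day 14, or to the last observed day.

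**Protocol.** Table 9 in Section 9.4 sets one rule for all three measures, including the CFU (0-2) and (2-14) slopes: "linear and bilinear regression models will be fit, and the better fit model based on lower AIC will be used to estimate" them. Section 9.4.1.2 adds that TTP and LAM are to be assessed in the same way as CFU. SAP Section 8 declares no change from the protocol's planned analyses.

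**The concern.** The protocol lists activity in the first two days and in the remaining twelve as separate secondary endpoints. A (0-2) slope is informative only if it can differ from the overall slope. For every participant whose TTP or LAM profile is fitted by a line, it cannot.

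The protocol's rationale for TTP and LAM (Section 4.2) is that they are easier to run, and that insight into whether they could replace solid culture would be useful. A reader will therefore set the three BA(0-2) results side by side. With different estimators, a gap between CFU and TTP could come from the assay or from the fitting rule, and the reported results will not show which.

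**Working it through.** **1. Algebra (no assumptions).** Under y = α + βt the average slope from a to b is [β(b - a)]/(b - a) = β. So BA(0-2) = BA(2-14) = BA(0-14) = β whenever the line is selected.

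**2. The missing formula.** With an estimated node κ, the interval averages of the fitted curve would be
- BA(0-2) = [min(κ,2)·β1 + max(2-κ,0)·β2]/2
- BA(2-14) = [max(κ-2,0)·β1 + (14-max(κ,2))·β2]/12

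The SAP gives neither. They are used below as the natural reading. They reduce to β1 and β2 only if κ = 2.

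**3. What the line returns in a biphasic profile.** Take noise-free slopes -0.30 to Day 2 and -0.05 after, on days 0 to 14. Regressing min(t,2) on t gives Sxy = (1-7)·1 + 2·Σ(t-7) over t = 2 to 14 = -6 + 2·13 = 20. Sxx = 280, so the ratio is 20/280 = 0.0714. The fitted line has slope -0.05 + (-0.30 + 0.05)·0.0714 = -0.068. That value would be reported for the early phase, where the true slope is -0.30.

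**4. How far the two rules differ (simulation).** Inputs from the SAP: 15 time points, screening value averaged over two samples, AIC with 3 parameters (line) or 5 (bilinear), 1 < κ < 14. Inputs assumed, because the documents give none: slopes, node and residual SD. Runs had 1,500 to 4,000 participants per scenario. Where a range is shown it spans repeated runs, or the SDs listed.

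| Assumed truth | Residual SD | True (0-2) | AIC rule | Node fixed at 2 |
|---|---|---|---|---|
| log LAM -0.30/-0.05, node Day 2 | 0.2 | -0.30 | -0.241 | -0.300 |
| same | 0.3 | -0.30 | -0.195 to -0.201 | -0.297 to -0.301 |
| same | 0.5 | -0.30 | -0.163 | -0.298 |
| log LAM -0.20/-0.08, node Day 2 | 0.3 | -0.20 | -0.129 | -0.199 |
| log LAM -0.30/-0.05, node Day 4 | 0.3 | -0.30 | -0.319 to -0.325 | -0.471 to -0.475 |
| log LAM -0.30/-0.05, node Day 5 | 0.3 | -0.30 | -0.326 | -0.507 |
| TTP 1.0/0.3, node Day 2 | 1.0-1.5 | 1.00 | 0.60 to 0.68 | 0.99 to 1.00 |
| TTP 1.0/0.3, node Day 4 | 1.0 | 1.00 | 1.03 | 1.47 |
| log LAM linear, -0.10 | 0.3 | -0.10 | -0.103 | -0.105 |

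Relative gaps: (0.30 - 0.20)/0.30 = 33% for LAM at node Day 2 with SD 0.3; (0.475 - 0.325)/0.325 = 46% at node Day 4; (1.47 - 1.03)/1.03 = 43% for TTP at node Day 4.

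**5. How often the phases collapse.** In the LAM -0.30/-0.05, node Day 2 case the line is chosen for 21%, 45% and 60% of participants at SD 0.2, 0.3 and 0.5. In the TTP node Day 2 case it is 53-66%. When the bilinear model wins in the simulated profiles with a Day 2 node, its node lies more than 0.1 day from Day 2 in 81-96% of fits, so the missing formula matters for most of the rest.

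**6. The later phase.** With the node at Day 2, BA(2-14) under the AIC rule is -0.055 to -0.058 against a true -0.050 for LAM, and 0.32 against 0.30 for TTP.

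**The case against.** The strongest reply has four parts.

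- **Direction.** A reader might infer that the AIC rule understates early activity by about a third. That holds only if the true node is at Day 2, the value the fixed model assumes. With a node at Day 4 the AIC rule is close to the truth and the fixed node overshoots; per-participant RMSE for LAM is 0.140 (AIC) against 0.217 (fixed). In a mildly biphasic case (-0.15/-0.08, node Day 2, SD 0.3) the AIC mean is biased (-0.108), yet its RMSE is lower (0.092 against 0.133). This stands: the documents support neither a one-sided bias nor the view that κ = 2 is the correct estimator.
- **Protocol.** TTP and LAM follow protocol Table 9; the CFU analysis in SAP 11.1.2 is what departs from it. This also stands. Consistency could equally be restored by returning CFU to Table 9, although the interval formulas would then have to be written for all three measures.
- **No planned comparison.** Replacement of solid culture is rationale text. The SAP plans no formal CFU-TTP-LAM concordance analysis, the slopes are in different units, and line plots by time point will show early change without any model. This limits the consequence, but same-named slopes in one report will still be read together.
- **Rank.** The endpoints are secondary, with no multiplicity adjustment and no success criterion. A reader might infer that the primary result is at risk; it is not, because BA_CFU(0-14) uses neither disputed rule.

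**Conclusion.** The inconsistency is real and rests on the text and step 1 alone. CFU phase slopes use a Day 2 node. TTP and LAM phase slopes use an AIC choice that makes both phases identical when the line wins, and that has no stated formula when the bilinear model wins with a node elsewhere.

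Its size rests on assumed inputs. In clearly biphasic data the two BA(0-2) estimators differ by about 30-50%, with the sign of the bias set by a node nobody knows in advance. If decline is truly linear their means agree. BA(2-14) is little affected in the Day 2 scenarios computed. The matter should be corrected before analysis, but it bears only on secondary endpoints and leaves the primary conclusion untouched.

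**What to change.** Use one estimator for the (0-2) and (2-14) slopes of CFU, TTP and LAM. The simplest route is to have SAP 11.2.1 and 11.2.2 refer to the κ = 2 model of 11.1.2 for these two intervals, and to 11.1.1 with its AIC choice for (0-14) only. The Appendix 4 code needs its response variable changed and its starting-value grid reset to the TTP and LAM scales. List the departure from protocol Table 9 in SAP Section 8 for all three measures, including the one already made for CFU.

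Cost: a few lines of SAP text and a declared change from the protocol. There is also a statistical price. If decline is truly linear, individual (0-2) slopes become more variable (SD about 0.13 against 0.07 for log LAM at residual SD 0.3). In the biphasic LAM case with a Day 2 node they are less variable (0.135 against 0.163). If the true node is not at Day 2, the fixed-node slopes mix the two phases, and the report should say so when interpreting BA(0-2).
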